So it have been planned to conduct an experimental clinical trial using combination of ivermectin and doxycycline for treatment of COVID 19 along with the other standard care. It would be a randomized double blind placebo controlled Trial. The study would be conducted on 200 confirmed cases of Covid- 19. Another 200 patients will receive placebo.

The primary outcome would be the Days required for the Clinical improvement of the patients from the day of randomization.

Data will be analyzed using SPSS 20. Unpaired t-test would be used for testing quantitative data and for testing qualitative data two sample z- test would be used. For the comparison between two groups Hazard ratio, Kaplan-Meire curve, binary logistic regression would be used to see the outcome. Result of the study and statistical analysis will be presented by tables, figures, graphs, diagrams, charts and photographs. All these will have own legends (i.e. title) and will be serially numbered. Discussion will be done on the basis of result obtained from the study and comparing with similar studies done at home and abroad. Summarization will be drawn after discussion. Conclusion will be drawn depending upon the results and discussion.

PART - D

INTRODUCTION

On 31 December 2019, the World Health Organization (WHO) was formally notified about a cluster of cases of pneumonia in Wuhan City¹. On 7 January the causative virus was isolated and its genome sequence was shared on 12 January. The cause of the severe acute respiratory syndrome that became known as COVID-19 was a novel corona virus, SARS-CoV-2². The virus Spread quickly through out the universe in quick succession. The World Health Organization (WHO) on March 11, 2020, has declared the novel Corona virus (COVID-19) outbreak a global pandemic³.

Phylogenetic analysis suggests that SARS-CoV-2 originated in animals, probably bats, and was transmitted to other animals before crossing into humans at the Huanan wet market in Wuhan City⁴⁻⁵. It was the year 1918, when a new flu pandemic launched worldwide The pandemic infected 3% to 5% percent of the world's population including remote Pacific islands and the Arctic. The Life expectancy dropped by about 12 years⁶. The fatal casualties of the diseased had reached the number of the fifty million victims⁷.

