Dosage of the drugs: Ivermectin 6 mg 2 tab stat, cap Doxycycline 100 mg 1 cap BD 5 days

Content of the placebo:

Placebo description of Ivermectin: Attached with Annexure 1

Product Name: Placebo Tablet of Ivec 6 Tablet

Batch No.: PB029

Mfg. Date: JUN 2020

Exp. Date: MAY 2022

Appearance: A pale yellow colored, round, standard bi-convex uncoated tablet with a bre line on one side and other side plain

Composition:

SL. No.	MATERIAL NAME	QUANTITY PER TABLET	PERCENTAGE PER TABLET
1.	Microcrystalline Cellulose (PH102)	63.355 mg	74.544 %
2.	Pregelatinised Starch (Starch 1000)	20.000 mg	16.500 %
3.	Sodium Starch Glycolate (Type A)	9.375 mg	7.500 %
4.	Anhydrous Citric Acid	0.013 mg	0.010 %
5.	Butylated Hydroxyanisol (BHA)	0.012 mg	0.010 %
6.	Pigment Blend Yellow PB0071	0.045 mg	0.036 %
7.	Colloidal Anhydrous Silica (Aerosil 200)	0.500 mg	0.400 %
8.	Magnesium Stearate	1.750 mg	1.400 %

Placebo Description of Doxycycline: Attached with Annexure II

Product Name: Placebo Capsule of Doxibac 100 Capsule

Batch No.: PB030

Mfg. Date: JUN 2020

Exp. Date: MAY 2023

Appearance: Hard gelatin capsule shell size #2 having white opaque body imprinted with popular logo in black ink and dark blue opaque cap containing white granular powder

Composition:

SL. No.	MATERIAL NAME	QUANTITY PER CAPSULE	PERCENTAGE PER CAPSULE
1.	Anhydrous Lactose	247.650 mg	88.440%
2.	Microcrystalline Cellulose (PH102)	7.350 mg	2.626%
3.	Sodium Starch Glycolate (Type A)	20.000 mg	7.143%
4.	Magnesium Stearate	5.000 mg	1.766%
5.	EHGC Shell Size #2 (Body: White Opaque, Cap: Dark Blue Opaque)	1 Pc.	---

Estimated study date: 01 June, 2020

Estimated primary completion date, 25 August 2020

Estimated study completion date: September, 2020

Inclusion Criteria:

- At least 18 years of age
- COVID-19 infection, confirmed by polymerase chain reaction (PCR) test within 3 days from enrollment
- Only mild and moderate COVID-19 infected cases
- Able to provide informed consent

Exclusion Criteria:

- Unable to take oral medication
- Pregnant or breast feeding lady
- Patients with severe COVID symptoms or admission in ICU/HDU

- Alanine Aminotransferase (ALT) or aspartate aminotransferase (AST) > 5 X upper limit of normal (ULN)
- On non-invasive positive pressure ventilation or mechanical ventilation at time of study entry
- Known hypersensitivity to Doxycycline or ivermectin or its components.

Research instruments:

1. Informed consent form.
2. Case record form

Primary Outcome Measure:

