The number of days required for clinical improvement

1. Early Clinical improvement of the patients
How many days it requires to become the patient completely symptoms free
[Time Frame: 7 days]
2. Late clinical recovery
How many days the symptoms persist
[Time Frame: 12 days]

Secondary Outcome Measure:

1. Percentage of patients having clinical deterioration.
Patients deteriorating to next level of severity, like moderate, severe and death
[Time Frame: 1 month]
2. Persistently positive for RT-PCR.
Percentage of Covid-19 Patients repeatedly become positive for RT-PCR for Covid-19
[Time Frame: 14 days]

Data collection technique:

Data will be collected by assigned. trained data collectors (Physician).

Patient will be enrolled according to defined inclusion and exclusion criteria in the current research. Informed written consent will be obtained from the patient or their relatives. Each patient participating in the trial will be uniquely identified, and information such as his name, address is recorded in the trial 'subject number list'. Only the principle investigator will be aware about the allocation of the drugs. The patients

and the data collectors will be unaware about the group allocation of the drugs. The Data will be reviewed by the co-investigators. It will be managed by principle and co-principle investigators in designated computer.

Clinical assessment (fever, cough, Anorexia, Temperature, pulse, blood pressure, respiratory rate, oxygen saturation) will be done every day. Routine investigation (CBC, ESR, CRP, Creatinine, RBS, SGPT, chest x-ray, D- Dimer) will be done at admission and at day 3, 5, 7, 10 and 14 day. In case of the clinical deterioration it would done according to necessity. RT-PCR will be done at day-0, Day 5, day 7 and day 14.

Standard care: both the experimental and placebo will receive the available standard of care, like-

- Paracetamol, Antihistamine, Cough suppressant, Vitamins
- Oxygen therapy according to indication and need
- Low molecular weight heparin according to indication
- Appropriate other broad spectrum antibiotics
- Other drugs for associated co- morbid condition

Management of the adverse events:

Drugs adverse effect will be monitored by a defined committee. The patient experiencing adverse effect of the drugs will be discontinued from the study. It will be managed with priority to the highest possible level by the hospital authority as well as the investigators.

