If the patient progresses from mild to moderate or severe disease, the study will be continued and available management of the appropriate severity will be immediately started. The patient will be monitored closely.

Data analysis:

Data will be analyzed by computer with the help of SPSS (Statistical Package for Social Sciences) version 20. To compare mean of the two group chi square will be used. Comparing drug outcome in between two group survival analysis by Kaplan-Meier curve will be done for the duration of recovery. Odds ratio will be formulated from linear logistic regression for early and late clinical recovery. Hazard ratio will be formulated from the cox regression analysis for severity conversion and persistence of the positivity. Crude odds ratio will be adjusted in cox proportional hazard ratio model. Each Ivermectin-Doxycycline plus standard of care group will be compared with the placebo plus standard care group using the log-rank test, hazard ratio and 95% CI. Participants who were lost to follow up, died, discontinue drugs due to adverse effect will censored on the last study day. All P values will be two-sided and will be shown without

adjustment for multiple testing. All analyses will be performed according to the intention to treat principle.

Dropout management: Intention to treat measure will be taken

Observation and Results:

Result of the study and statistical analysis will be presented by tables, figures, graphs, diagrams, charts and photographs. All these would have own legends (i.e. title) and will be serially numbered.

Discussion:

Discussion will be done on the basis of result obtained from the study and comparing with similar studies done at home and abroad.

Summary:

Summarization will be drawn after discussion.

Conclusion:

Conclusion would be drawn depending upon the results and discussion

Conflict of interest:

Popular pharmaceutical will only provide drugs and the placebo.
None of the investigators will receive remuneration from the pharmaceutical company.
They will not get any access to data profile.

Operational definition:

(According to WHO guideline)

Confirmed Covid-19:

Cases with positive RT-PCR for Covid 19 irrespective of symptoms.

Uncomplicated (mild) Illness

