These patients usually present with symptoms of an upper respiratory tract viral infection, including mild fever, cough (dry), sore throat, nasal congestion, malaise, headache, muscle pain, or malaise. Signs and symptoms of a more serious disease, such as dyspnea, are not present.

Moderate Pneumonia

Respiratory symptoms such as cough and shortness of breath (or tachypnea in children) are present without signs of severe pneumonia.

Severe Pneumonia

Fever is associated with severe dyspnea, respiratory distress, tachypnea (> 30 breaths/min), and hypoxia ($\text{SpO}_2 < 90\%$ on room air). However, the fever symptom must be interpreted carefully as even in severe forms of the disease, it can be moderate or even absent. Cyanosis can occur in children. In this definition, the diagnosis is clinical, and radiologic imaging is used for excluding complications.

Acute Respiratory Distress Syndrome (ARDS)

The diagnosis requires clinical and ventilatory criteria. This syndrome is suggestive of a serious new-onset respiratory failure or for worsening of an already identified respiratory picture. Different forms of ARDS are distinguished based on the degree of hypoxia. The reference parameter is the $\text{PaO}_2/\text{FiO}_2$:

- Mild ARDS: $200 \text{ mmHg} < \text{PaO}_2/\text{FiO}_2 \leq 300 \text{ mmHg}$. In not-ventilated patients or in those managed through non-invasive ventilation (NIV) by using positive end-expiratory pressure (PEEP) or a continuous positive airway pressure (CPAP) $\geq 5 \text{ cmH}_2\text{O}$.
- Moderate ARDS: $100 \text{ mmHg} < \text{PaO}_2/\text{FiO}_2 \leq 200 \text{ mmHg}$.
- Severe ARDS: $\text{PaO}_2/\text{FiO}_2 \leq 100 \text{ mmHg}$.

When PaO_2 is not available, a ratio $\text{SpO}_2/\text{FiO}_2 \leq 315$ is suggestive of ARDS.

Chest imaging utilized includes chest radiograph, CT scan, or lung ultrasound demonstrating bilateral opacities (lung infiltrates $> 50\%$), not fully explained by effusions, lobar, or lung collapse.

Clinical improvement Criteria

1. Body temperature remains normal for at least 3 days (ear temperature is lower than 37.5°C).

2. Respiratory symptoms are significantly improved.
3. Lung imaging shows obvious improvement in lesions.
4. There is no co-morbidities or complications which require hospitalization.
5. SpO₂, >93% without assisted oxygen inhalation.

8. FLOW CHART of Study workup:

Sl No	Activities						
		1 st	2 nd	3 rd	4 th	5 th , 6 th , 7 th	8 th

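### No inclusion criterion requires a symptom at randomisation, yet the primary outcome times the disappearance of symptoms, and the case record form omits two symptoms that define mild illness

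*Protocol*

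**What the plan says.** **Eligibility** (Protocol, section 4, Inclusion Criteria). There are four criteria: adult age, PCR confirmation, severity and consent. The two that matter here are "COVID-19 infection, confirmed by polymerase chain reaction (PCR) test within 3 days from enrollment" and "Only mild and moderate COVID-19 infected cases".

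**Definitions** (Protocol, Operational definition).
- Confirmed Covid-19: "Cases with positive RT-PCR for Covid 19 irrespective of symptoms".
- Mild illness: "These patients usually present with symptoms of an upper respiratory tract viral infection". The symptoms then named include malaise and muscle pain.
- Moderate: "Respiratory symptoms such as cough and shortness of breath (or tachypnea in children) are present without signs of severe pneumonia".
- There is no separate category for infection without symptoms.

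**Primary outcome.** The summary before Part D gives it as "Days required for the Clinical improvement of the patients from the day of randomization". Under Primary Outcome Measure, the first item is "How many days it requires to become the patient completely symptoms free", and the second counts how long symptoms last. The five-item Clinical improvement Criteria, at the end of the operational definitions, are a different standard. They begin with "Body temperature remains normal for at least 3 days" and also call for improvement in respiratory symptoms and on lung imaging.

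**Data capture** (Case Record Form, Clinical Feature). Fourteen symptoms are scored yes or no at enrolment and daily to day 14. A patient can be marked no on all fourteen at enrolment. Malaise and muscle pain are not among them.

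**The concern.** A time-to-recovery outcome has meaning only for a patient who has something to recover from. The eligibility text lets in two kinds of patient who do not: a PCR-positive person without symptoms, who can be placed only in the mild category, and a patient whose symptoms resolved between onset and randomisation. For both, the number of days to being symptom free is zero or undefined whichever treatment is given. The protocol does not say how they are to be handled. If they count as recoveries they raise the recovery rate in both arms and shrink the difference between them.

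The case record form adds a separate fault that needs no assumption about who is enrolled. A patient who qualifies on malaise or muscle pain alone is recorded as symptom free on entry. Any patient in whom one of these is the last symptom to go is recorded as recovered too early.

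**Working it through.** **1. Can a symptom-free patient be enrolled?** PCR confirmation holds whether or not symptoms exist. Moderate disease cannot be met without respiratory symptoms, so the gap does not arise there. The mild definition says what patients usually have, which describes rather than requires. No criterion refers to the day of randomisation or to time since onset. The gap is therefore real but confined to the mild category.

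**2. Does such a patient already meet the endpoint?** On the first primary item, yes: time runs from randomisation and the patient is free of symptoms at that point. On the five-item criteria, not automatically: three days of normal temperature must be documented, and a patient with no respiratory symptoms or lung lesions cannot show that they improved. The outcome is poorly defined for this patient under either reading.

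**3. Reproducing the planned size.** Inputs from Estimated enrollment (section 4): rates 0.40 and 0.58, α = 0.05, β = 0.20. Data analysis states two-sided P values.

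h = |arcsin √0.40 − arcsin √0.58| = 0.1810

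N = ½ × (2.805 / 0.1810)² = 120.05, rounded up to 121. The protocol's figure is reproduced.

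**4. Illustrating the dilution.** Let f be the share of each arm that is symptom free at entry and counted as recovered. The documents do not give f, so the range is an assumption. I also assume that 40% and 58% apply to the symptomatic patients and that the outcome is binary.

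- Diluted rate: p′ = f + (1 − f)p
- Power = Φ(h′√(2n) − 1.96)

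Example, f = 20%, n = 200: the rates are 0.20 + 0.80 × 0.40 = 0.520 and 0.20 + 0.80 × 0.58 = 0.664; h′ = 0.1471; 0.1471 × 20 − 1.96 = 0.982; power 83.7%.

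The last column uses 200 less the protocol's 20% loss: 200 × 0.80 = 160.

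| f | Rates | Difference (points) | Power, 200 per group | Power, 160 per group |
|---|---|---|---|---|
| 0 | 0.400 vs 0.580 | 18.0 | 95.2% | 89.9% |
| 10% | 0.460 vs 0.622 | 16.2 | 90.4% | 83.2% |
| 20% | 0.520 vs 0.664 | 14.4 | 83.7% | 74.9% |
| 30% | 0.580 vs 0.706 | 12.6 | 75.2% | 65.6% |

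Power drops just below 80% at about f = 25% with 200 per group (79.6%) and at about f = 15% with 160 (79.2%).

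**5. If zero-time patients add no time at risk.** Data analysis plans Kaplan-Meier curves and the log-rank test for duration of recovery. If these patients leave before the first risk set, the loss is roughly that of a smaller sample, n(1 − f), with the 18-point difference intact. Starting from 200 per group this leaves 180, 160 and 140, with power 93%, 90% and 86% for f = 10%, 20% and 30%. Starting from 160 it is 86.7%, 82.5% and 77.3%.

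**The case against.** **Severity is a separate entry test.** A reader might infer from the confirmed-case definition that a positive PCR alone gains entry. It does not: that sentence concerns laboratory confirmation, and a patient must also have mild or moderate disease. This stands, and it narrows the gap to the mild category.

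**The form points to symptomatic inpatients.** It asks for the date symptoms began and the hospital admission date, and the investigations are timed from admission. It also asks about an epidemiological link, from which one might infer that symptom-free contacts will be recruited, but that is a routine demographic item. These fields make enrolment of contacts less likely. They do not exclude patients whose symptoms had already ended.

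**The size is not derived from the trial.** This stands. The protocol does not define the response behind 40% and 58%. If those rates already describe the enrolled mix, there is no shortfall against the plan. One could also work at 121 per group and report power as low as 53.7% (f = 30%), but the protocol plans to enrol 200 per group.

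**The patients can be identified.** Because analysis is by intention to treat, a reader might infer that nothing can be done about them later. Their symptoms are recorded at enrolment, so they can be set apart on baseline data, and an analysis plan that is not shown may do so. That would settle their handling, but it would not recover symptoms the form never collected.

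**Conclusion.** The point holds as a should-fix. The eligibility text allows patients with nothing to recover from on the first primary item, and the case record form can score a patient as recovered while malaise or muscle pain persists. Both follow directly from the text.

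The effect on power depends on f, which is unknown, on the protocol's rates applying to symptomatic patients, and on a binary analysis. On those assumptions, the planned enrolment keeps at least 80% power at f = 20% without losses, and at f = 10% after 20% loss. Larger shares would cost more, though less under the log-rank test if zero-time patients contribute no time at risk. The effect of the two missing symptoms cannot be sized from the documents.

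A reader might also infer a risk of a false positive result. The documents do not support that: with 1:1 randomisation such patients are balanced between arms in expectation, so the consequence is attenuation and lost power, not inflated type I error.

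**What to change.** 1. Reword the third inclusion criterion along these lines: *mild or moderate COVID-19 with at least one symptom listed on the case record form present on the day of randomisation.*
2. State beside the confirmed-case definition that it covers laboratory confirmation only and does not by itself confer eligibility.
3. Add malaise and muscle pain to the daily symptom grid, so that the symptoms that define mild illness are the ones followed to resolution.
4. Reconcile the symptom-free primary item with the five-item Clinical improvement Criteria, so that one definition governs the primary outcome.

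**Cost.** One inclusion line, one sentence, two form rows and one decision on the endpoint, all needed before enrolment. Recruitment would be slightly slower. The trial would also lose symptom-free PCR-positive patients, who carry no information on time to symptom resolution but would have informed the secondary outcomes of clinical deterioration and persistent PCR positivity.

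**Alternative.** If the sponsor wishes to keep those patients, restrict the primary time-to-recovery analysis to patients with a symptom recorded at enrolment before treatment, and retain everyone for the secondary outcomes. Because the subset is defined before treatment, the randomised comparison is preserved within it. The intention-to-treat statement in Data analysis would need to say so.

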Clinical Feature

Trait			Follow-up Yes-1, No-2												
	On Enrollment		D 2	D3	D4	D-5	D-6	D-7	D-8	D-9	D-10	D-11	D-12	D-13	D-14
Fever	 Yes	 No													
Cough	 Yes	 No													
Running nose	 Yes	 No													
Sputum	 Yes	 No													
Respiratory distress	 Yes	 No													
Sore throat	 Yes	 No													
Hoarseness of voice	 Yes	 No													
Chest pain	 Yes	 No													
Diarrhoea	 Yes	 No													
Vomiting	 Yes	 No													
Anosmia	 Yes	 No													
Anorexia	 Yes	 No													
Headache	 Yes	 No													
Confusion	 Yes	 No													

Obsrvation

Trait		Follow-up Yes-1, No-2												
	On Enrollment	D 2	D3	D4	D-5	D-6	D-7	D-8	D-9	D- 10	D- 11	D- 12	D- 13	D- 14
Temperature														
Pulse rate														
BP														
Respiratory Rate														
Oxygen saturation														
Co- Morbidity	DM/HTN/ IHD/ HF/ CKD/CLD/Asthma/COPD/Malignancy/ CTD													

Investigations Profile

Trait	Value					
	Admission	D-3	D-5	D-7	D-10	D-14
Hb						
WBC						
Neutrophil						
Lymphocyte						
Platelet						
ESR						
CRP						
RBS						
Creatinine						
SGPT						
D-Dimer						
Na						
K						
ECG						
Covid-19 RT-PCR						

Radio-Imaging

Trait	Findings
Chest X-Ray CT Chest	Normal/ Consolidation (unilateral or bilateral) / Patchy opacity Consolidation/ Ground Glass Opacity/nodule/ multifocal

Principal Investigators:

Date:

Annexure-1

Popular Pharmaceuticals Ltd.

QUALITY ASSURANCE DEPARTMENT

Certificate of Analysis

Product Name: Placebo Tablet of Imec 6 Tablet

Batch No.: PB029

Mfg. Date: JUN 2020

Exp. Date: MAY 2022

Appearance: A pale yellow colored, round, standard bi-convex uncoated tablet with a break line on one side and other side plain

Composition:

SL. No.	MATERIAL NAME	QUANTITY PER TABLET	PERCENTAGE PER TABLET
